The ESP block procedure - participant consent will be performed on the day of surgery by one of the research investigators in the pre-operative surgical unit (PSU). Randomization is not required because all participants will be undergoing the same protocol. All participants will also be undergoing cardiac surgery by the same surgeon. Routine care will be performed for the placement of the ESP block and is described as follows: the ESP block will be performed by the acute pain service, which will have members that are not involved with the research. Adequate block placement will be confirmed by one of the investigators via ultrasound images that are captured during the procedure. The participant, who is already in a patient gown with an intravenous line (IV) in place, will be positioned sitting on the side of the patient bed. Vital sign monitoring with pulse oximetry and blood pressure cuff will be connected. The participant will be given intravenous midazolam to reduce anxiety and enhance comfort during the ESP block procedure. Full aseptic precautions will be taken with personal protective equipment and bactericidal preparation with chlorhexidine. An ultrasound probe will be placed lateral to the patient's upper back and the ideal location of medication injection will be identified on an ultrasound image (which is superficial to the transverse processes of the thoracic vertebral bodies and deep to the erector spinae muscle). The skin will be made numb with lidocaine prior to insertion of a larger needle (Tuohy needle); the proceduralist will direct the Tuohy needle to the desired target under ultrasound guidance and 25 cc 0.25% ropivacaine will be delivered through that needle. A continuous nerve catheter will then be inserted through the Tuohy needle to allow for continuous delivery of medication if desired. The Tuohy needle will be removed, and the nerve catheter will be secured in place with adhesive dressing. Cardiac surgery will require bilateral (left and right) nerve catheter placement, and therefore, upon completion of one side, the ESP block will be performed on the other side. The estimated time needed for a bilateral ESP block procedure is 30 minutes. After the completion of the ESP block procedure, the participant will undergo their planned cardiac surgery procedure, which typically takes many hours.

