Initiation of continuous nerve catheter infusions (alteration of standard care) - this component of care will be different than routine care. Nerve catheter infusions are typically initiated at the end of the surgical procedure at a concentration and rate of 0.2% ropivacaine at 8-10 cc/hr.

The study protocol will direct the nerve catheter infusions to run at 1 cc/hr; this rate will allow the nerve catheters to remain open and patent but will not significantly interrupt or alter the quality of the research data collection. The operating room team and ICU staff will be notified about the patient's participation in the study and will have information available regarding the alterations from routine practice that would be required for this study.

Research protocol, part 1 - the research protocol and data collection will begin on the afternoon of post-operative day 1 (the day after surgery) in the cardiac surgery intensive care unit (CSICU). Typically, cardiac surgery patients will be sedated and have a breathing tube in place until the morning of post-operative day 1. This delayed timing of the study will allow the participant to stabilize after removal of the breathing tube. Although written consent has already been obtained, a research investigator will obtain a verbal reaffirmation from the participant and update the CSICU team before proceeding.

Per routine, the participant will have vital sign monitors connected and have an arterial line in place that will allow for collection of blood samples for laboratory testing. The nerve catheter infusions will be suspended and the research protocol will begin in the CSICU as follows: the investigator will administer 25 cc 0.25% ropivacaine through each nerve catheter (totaling 50 cc 0.25% ropivacaine) and record the time of administration on a data collection sheet. Either the investigator or study assistant will collect arterial blood samples at the following intervals after the medication bolus: 10 minutes, 15 minutes, 30 minutes, 45 minutes, 60 minutes, 90 minutes, 2 hours, and 4 hours. The blood samples will be labeled with a patient ID sticker and will also contain the study ID number and the time interval that corresponds with the blood sample. The samples will be stored in a designated ice cooler that will be delivered to the clinical laboratory.

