During this first portion of sample collection, the secondary outcome of dermatomal analgesia and duration will be assessed. At the 60-minute interval, a study investigator will test areas of numbness performing a pinprick test and using a dermatomal map to mark the areas of numbness. For the pinprick test, the investigator will use a pointed object that is sharp enough to elicit a sharp sensation but blunt enough that it does not cause skin damage; the participant will be asked to provide comparison of the sensation of the pointed object when it is applied to an area that is not expected to be numb (like the palm) versus an area that is expected to be numb (like the chest and thorax). At the 90-minute, 2 hour, and 4 hour intervals, the participant will be asked if the numbness from the nerve block has gone away. If the resolution of numbness occurs between the time intervals, the participant will be asked to look at the clock and remember the time at which the difference was felt. It is expected that at the 4-hour interval, the serum ropivacaine level will be approaching or have reached the baseline level before the bolus was given.

Research protocol, part 2 - at the 4-hour interval (4 hours after the initial bolus), both nerve catheter infusions will be resumed at a concentration and rate of 0.2% ropivacaine at 10 cc/hr. Either the investigator or study assistant will collect arterial blood samples at the following intervals after the start of the infusion: 60 minutes, 2 hours, 4 hours, 8 hours, 12 hours, 24

hours. Dermatomal analgesia assessment will be performed by one of the research investigators at the 24-hour mark. After this assessment, the research protocol will be considered complete and routine care by the CSICU and acute pain service will resume. The researchers will collaborate with the health care teams during the study protocol if this becomes necessary to maintain patient safety and comfort.

The collected blood samples are viable for one week if they are refrigerated and one month if they are frozen. Free and total ropivacaine levels will be determined for each sample by the clinical laboratory and this information will be distributed to the research investigators in a way that protects patient health information and will be recorded securely onto a data collection sheet. The data for this sheet can then be used for statistical analysis and creation of a pharmacokinetic profile for the ESP block (both bolus and infusion curves).

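### No blood sample or pinprick map is taken just before the study bolus, so bolus Cmax and the 60-minute map cannot be separated from the effect of ropivacaine already given

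*Combined protocol and SAP*

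**What the plan says.** Under *The ESP block procedure*, each side receives a pre-operative block: "25 cc 0.25% ropivacaine will be delivered through that needle". Both sides are blocked.

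Under *Initiation of continuous nerve catheter infusions*, "The study protocol will direct the nerve catheter infusions to run at 1 cc/hr". The protocol says that this rate "will not significantly interrupt or alter the quality of the research data collection". It gives no concentration for this infusion and does not say whether 1 cc/hr applies to each catheter or to both together.

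Under *Research protocol, part 1*, on the afternoon of the day after surgery, the text goes straight from stopping the infusion to dosing: "The nerve catheter infusions will be suspended and the research protocol will begin in the CSICU as follows: the investigator will administer" the bolus, 50 cc of 0.25% in all. No washout interval is stated. Blood is drawn at set times "after the medication bolus: 10 minutes, 15 minutes, 30 minutes, 45 minutes, 60 minutes, 90 minutes, 2 hours, and 4 hours". The one map in this part is described so: "At the 60-minute interval, a study investigator will test areas of numbness performing a pinprick test". The comparison within that test is with another body site, such as the palm. At 4 hours the expectation is that "the serum ropivacaine level will be approaching or have reached the baseline level before the bolus was given".

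*Data analysis* compares Cmax and Tmax between bolus and infusion and mentions no baseline correction.

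**The concern.** The first specific aim is a concentration–time curve with Cmax and Tmax; the second is the distribution and duration of analgesia. Each asks what follows the study bolus, but neither has a reference point before it.

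The protocol refers to a pre-bolus baseline level and then schedules no sample that would give it. It also states, without a planned check, that the 1 cc/hr infusion does not matter. A time-0 sample would test both statements.

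Three things are at stake:

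- Cmax read as the result of the study dose alone would include an unknown amount of earlier drug.
- The palm shows the participant what normal sensation is like. It cannot distinguish numbness present before the bolus from new numbness. The later questions about whether numbness has gone lack the same reference.
- The expected return to baseline by 4 hours cannot be checked.

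Once the bolus is given, the missing sample and map cannot be recovered.

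**Working it through.** The protocol gives no figure of its own to reproduce. The omission is a matter of reading the schedule; the arithmetic below only shows how large the effect could be.

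**Inputs from the protocol**
- Pre-operative block: 2 × 25 cc × 2.5 mg/cc = 125 mg.
- Study bolus: 50 cc × 2.5 mg/cc = 125 mg, the same amount.
- Blood samples: 8 in part 1, all after the bolus, and 6 in part 2; 14 in total.

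**Assumptions, not in the protocol**
- One compartment with linear kinetics.
- Elimination half-life 2, 3, 4, 6 or 8 h.
- Absorption either instant or first-order with half-life 0.25, 0.5 or 1 h.
- 1 cc/hr of 0.2% fluid (2 mg/cc) for T = 16 or 24 h, so the rate r is 4 mg/h if the figure is per catheter or 2 mg/h if it is the total.
- Block 6 h before the infusion starts.

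**Instant absorption.** With k = ln 2 / half-life, the amount present just before the bolus is

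B = (r/k) × (1 − exp(−kT)) + 125 × exp(−k(T + 6)).

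Example with half-life 4 h, T = 16 h, r = 4: k = 0.1733; infusion part 23.08 × 0.9375 = 21.6 mg; block part 125 × exp(−3.81) = 2.8 mg; B = 24.4 mg, and 24.4/125 = 19.5% of the study bolus.

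**First-order absorption.** Per unit dose, the amount in the body at time t is

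f(t) = ka/(ka − k) × (exp(−kt) − exp(−ka t)),

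where ka = ln 2 / absorption half-life. An infusion is the integral of f over its duration. Cmax is the largest value at the eight listed sampling times, computed with and without the earlier drug; volume cancels in the ratios.

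Same example with absorption half-life 0.5 h:
- The bolus-only peak is 92.3 mg at 1.5 h. Earlier drug adds 21.1 mg at that time, giving 113.4 mg, and 113.4/92.3 = 1.23, an excess of 23%.
- The time-0 amount is 24.6 mg. Plain subtraction gives 113.4 − 24.6 = 88.8 mg, 4% below 92.3, because the earlier drug has partly cleared by the time of the peak.
- The 4-hour amount is 84.8 mg, and 84.8/24.6 = 3.4 times the pre-bolus amount.

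**Ranges over all scenarios** (5 elimination half-lives × 2 durations × 3 absorption half-lives = 30 per infusion rate under first-order absorption)

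| Quantity | 1 cc/hr per catheter | 1 cc/hr in total |
|---|---|---|
| Pre-bolus amount as share of 125 mg, instant absorption | 9–43% | 5–29% |
| – from the 1 cc/hr infusion alone | 9–32% | 5–16% |
| – from the block alone | 0–15% | 0–15% |
| Observed Cmax above bolus-only Cmax, first-order | 11–46% | 5–31% |
| Scenarios in which the sampled Tmax moves | 4 of 30 | 3 of 30 |
| Time-0 subtraction falls below bolus-only Cmax by | 2–13% | 1–10% |
| 4-hour amount ÷ pre-bolus amount, both absorption models | 2.4–4.5 | 3.2–8.6 |

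An excess of 46% means that earlier drug is 0.46/1.46 = 32% of the observed peak; the rest is the study bolus. In a separate run with slower absorption (half-life up to 4 h, block 28 h and infusion 20 h before the bolus, r = 4), the share of the observed peak due to earlier drug was about 10–47%.

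**The case against.** The strongest case against is that the study's safety question survives. Closeness to toxic levels depends on total concentration, which is measured, and the aims do not promise a bolus-only Cmax. This stands. A reader might infer that bolus Cmax is invalid or cannot be credited to the bolus at all. The documents do not support that: in every modelled scenario more than half of the observed peak is the study bolus. What is lost is the ability to separate the earlier contribution, and so to carry the result over to a patient without earlier ropivacaine.

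It can also be said that the sizes rest on assumed kinetics, and that the block was given the day before. Both are fair. The results run from 5% to 46%, so they do not show that the protocol's statement about the 1 cc/hr rate is wrong, only that it goes untested. Likewise, they do not establish that levels fail to return to baseline by 4 hours.

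Nothing in the documents indicates residual numbness on the afternoon of day 1. That the 60-minute map is contaminated is a possibility, not a finding.

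Finally, a reader might extend the point to the infusion phase. Drug carried into the early infusion samples comes mainly from the study bolus, which a time-0 sample would not remove. The level at infusion start is in fact measured, by the 4-hour sample. The variable left unnamed for the Kolmogorov–Smirnov test is also a separate matter.

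**Conclusion.** The concern holds in this form: earlier ropivacaine precedes the study bolus, no sample or map is taken immediately before it, and the protocol relies on a baseline level that will not exist in the data. That much follows from the text and needs no assumption.

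Observed Cmax stands as total exposure. The contribution of earlier drug can be neither separated nor shown to be negligible, pre-existing numbness could be counted in the 60-minute map, and the 4-hour expectation, which is not an endpoint, cannot be checked. The size is unknown. The 5–46% excess in Cmax and the few shifts in sampled Tmax are illustrations that depend on the assumed half-lives, infusion concentration, rate and timing. The change should be made before data collection, but its absence would not invalidate the study.

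**What to change.** In *Research protocol, part 1*, add one arterial sample (time 0) and one pinprick map, both immediately before the study bolus. In *Data analysis*:

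- Report observed Cmax together with a baseline-adjusted Cmax, and state that plain subtraction of time 0 over-corrects (by about 1–13% in the scenarios above). Subtracting a constant leaves Tmax as observed.
- Report the 60-minute map as change from the pre-bolus map.
- Compare the 4-hour level with time 0 within each participant.

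As a minor labelling point, name the existing 4-hour sample as the infusion starting level. This needs no extra blood.

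Modelling of residual drug could be an optional sensitivity analysis. It would need the block time and the start, stop, rate and concentration of the earlier infusion. For the study bolus the plan says to "record the time of administration on a data collection sheet"; it mentions no such record for the earlier drug.

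The cost is one extra tube per participant from the arterial line already in place (8 + 6 + 1 = 15 instead of 14; with free and total levels, 30 determinations instead of 28) and a short extra bedside test, assumed to take a few minutes. Dosing is unchanged. The fix does not resolve carry-over into the infusion phase or the unnamed test variable.

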Pharmacokinetic profile and dermatomal coverage of the erector spinae plane block - a comparison of bolus dosing and continuous infusion

Principal investigator: [name]., Assistant Professor, Virginia Commonwealth University Department of Anesthesiology

NCT number: not yet available

IRB approval date: March 6, 2019

Date of document: March 7, 2019

Introduction

Background

Muscle plane blocks are a fairly new regional anesthesia technique and are increasing in popularity. The most recent muscle plane block, termed the erector spinae plane (ESP) block, was developed to optimize pain control for thoracic surgery while minimizing the risks associated with paravertebral and epidural blocks. Numerous case reports have advocated for its use¹⁻⁴.

Significance of the research

In comparison to traditional neuraxial and peripheral nerve block approaches, a successful ESP block requires a higher volume of local anesthetic. Therefore, the optimal volume to produce analgesia from an ESP block may result in a plasma local anesthetic concentration that approaches toxic levels. Pharmacokinetic studies have been performed with muscle plane blocks, such as the quadratus lumborum block and transversus abdominus plane block^{5,6}; however, the pharmacokinetic profile of the ESP block has not yet been measured or studied. This study will demonstrate how quickly and closely toxic levels are reached when a routine dose of ropivacaine is given for the ESP block and will also assess for areas of numbness created by the ESP block when routine doses are administered.

Specific aims of the project

- Create plasma ropivacaine concentration-time curves after performance of an ESP block via bolus and continuous infusion into the ESP compartment. The concentration-time curves will include the peak serum concentration of ropivacaine (C_{max}) and the time required to reach maximum plasma concentration (T_{max}).
- Determine the dermatomal distribution and duration of analgesia created when ESP block is performed via ropivacaine bolus versus continuous ropivacaine infusion.

Methods

Study design

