This study will use clinical laboratory tests to objectively measure serum ropivacaine levels after an erector spinae plane (ESP) block is performed on patients undergoing cardiac surgery. During an ESP block, ropivacaine is typically injected into a muscle plane that is deep to the erector spinae muscle and superficial to the transverse process of the thoracic vertebral body; subsequently, the ropivacaine is absorbed into the bloodstream, at which time measurements can be taken. Secondary measurements will include distribution and duration of numbness created by the ESP block.

Description of procedures

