Data analysis

A two-sample Kolmogorov-Smirnov test will be used to determine the difference between the distributions of the bolus arm and the infusion arm. T_{max} and C_{max} of the two arms will be analyzed with an unpaired t-test. A logrank test will be used to assess the difference between the duration of analgesia created by the bolus arm and the infusion arm.

Institutional board approval

The protocol has been approved by Virginia Commonwealth University Institutional Review Board (Study ID HM20014803).

Literature cited

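### The Kolmogorov-Smirnov test and the unpaired t-test treat two consecutive phases in the same patients as independent arms, and the variable for the first test is not named.

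*Combined protocol and SAP*

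**What the plan says.** **The test.** Data analysis: "A two-sample Kolmogorov-Smirnov test will be used to determine the difference between the distributions of the bolus arm and the infusion arm". The next sentence applies an unpaired t-test to T_max and C_max of the two arms. A third applies a log-rank test to duration. Pairing and repeated measures are not mentioned.

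**The design.** Description of procedures: "Randomization is not required because all participants will be undergoing the same protocol". In Research protocol, part 1, each patient receives the bolus through both catheters. In part 2 the same patient goes on to the infusion: "at the 4-hour interval (4 hours after the initial bolus), both nerve catheter infusions will be resumed".

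**What could be compared.**
- Coverage. The second specific aim is: "Determine the dermatomal distribution and duration of analgesia created when ESP block is performed via ropivacaine bolus versus continuous ropivacaine infusion". Study design adds: "Secondary measurements will include distribution and duration of numbness created by the ESP block". The bolus assessment is described as follows: "At the 60-minute interval, a study investigator will test areas of numbness performing a pinprick test and using a dermatomal map". The infusion assessment is made at 24 hours.
- Concentration. Free and total levels are measured in every sample. Bolus samples are taken "after the medication bolus: 10 minutes, 15 minutes, 30 minutes, 45 minutes, 60 minutes, 90 minutes, 2 hours, and 4 hours". Infusion samples are taken "after the start of the infusion: 60 minutes, 2 hours, 4 hours, 8 hours, 12 hours", with a last one at 24 hours.

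**The concern.** A two-sample KS test and an unpaired t-test both need two independent groups. Here the groups are the same people measured twice in a fixed order. The distribution to be compared is also left open, and the consequence depends on it.

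If it is coverage, the between-regimen comparison in the second aim would be made with a test likely to miss a real difference. If it is concentrations pooled over time, the test could reject because the two phases were sampled at different times, and the result would say little about bolus against infusion.

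**Working it through.** The documents give no sample size, SD, correlation, effect size or significance level, so there is no planned figure to reproduce. The dependence and the sampling overlap follow from the text. The power figures rest on assumed inputs and a two-sided 5% level.

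**1. Independence.** One cohort, one protocol, bolus then infusion: each patient contributes to both samples. This holds for any variable.

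**2. Which variable.** For coverage: the second aim uses the word distribution for dermatomes, and no other listed test covers them. For concentration: the KS sentence stands directly before the C_max and T_max sentence, which separates it from duration, and no other test covers the curves. The text does not decide between them.

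**3. Coverage reading.** Each patient gives one assessment per phase. Model: rounded bivariate normal dermatome counts, mean 6, SD 2, shift 2, n = 10.

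| Test | Correlation 0 | Correlation 0.5-0.7 |
|---|---|---|
| Two-sample KS, exact | 16% | 10%-12% |
| Unpaired t-test | not used | 59%-61% |
| Exact signed-rank | not used | 74%-90% |

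- KS to unpaired t-test, both ignoring pairing: 59 - 12 = 47 to 61 - 10 = 51 points.
- Unpaired t-test to signed-rank: 74 - 61 = 13 to 90 - 59 = 31 points. This is nearer the cost of ignoring pairing.
- KS is weak here even with independent groups (16%). With 10 per group and no ties, its exact p-value is 2 × C(20,4)/C(20,10) = 2 × 4,845/184,756 = 0.052 at a maximum gap of 0.6, and 2 × C(20,3)/C(20,10) = 2 × 1,140/184,756 = 0.012 at 0.7. A gap of 0.7 is therefore needed, and the attainable level is about 1.2%. Ties lower it further.
- Other sizes, same shift, SD and correlations: n = 20, KS 55% against signed-rank 98%-99.9%; n = 6, 9% against 21%-32%.
- Limits of the paired test: at a 1-dermatome shift and n = 10, signed-rank power is about 22%-35%. With five non-zero differences its smallest two-sided p-value is 2/2^5 = 0.0625, so with five or fewer it cannot reach 0.05.

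**4. Pooled-concentration reading.** There are 8 bolus and 6 infusion samples per patient, 14 in all. The schedules share only 1, 2 and 4 hours, which accounts for 3 + 3 = 6 samples; the other 8 have no counterpart. KS ignores sampling time, so schedule and regimen are mixed.

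Dependence alone can also push the error rate either way. With n = 20, no difference between phases and assumed within-phase intraclass correlation 0.3-0.7, the nominal 5% test rejects in:
- 20%-41% of trials if patient effects are uncorrelated between phases;
- 11%-25% at between-phase correlation 0.5;
- 0.3%-2.8% at correlation 1.

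**5. Unpaired t-test.** With equal variances, the true variance of the mean difference is 2σ²(1 - r)/n, and the test uses 2σ²/n. The standard error is too large by 1/√(1 - r): 1/√0.5 = 1.41 and 1/√0.3 = 1.83. At n = 10 the simulated size is 0.9% and 0.2%.

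**6. Carry-over.** Research protocol, part 1 expects the 4-hour level to be only near or at its pre-bolus value. The bolus is 50 × 2.5 = 125 mg. The infusion is 10 × 2 = 20 mg/h per catheter, so 40 mg/h if the stated rate applies to each catheter and 20 mg/h if it is the total. With assumed first-order absorption (half-life 15 minutes), residue changes the bolus-to-infusion AUC ratio over 1-4 hours:
- at 40 mg/h, from 1.07 to 0.84 (elimination half-life 2 h) and from 1.34 to 0.69 (8 h);
- at 20 mg/h, from 2.15 to 1.39 and from 2.68 to 0.92.

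At the 24-hour coverage assessment, residue is at most 2.8% or 5.4% of the modelled level, respectively.

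**The case against.** **A reader might infer that coverage is plainly the KS variable.** The text does not support that. The second aim and Study design put distribution next to duration, but Data analysis does not: the C_max and T_max sentence lies between, and the KS sentence never mentions dermatomes. Both readings stay open.

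**A reader might blame the whole power gap on lost pairing.** The zero-correlation result rules this out: KS has little power at n = 10 even when the groups are independent. Pairing accounts for the smaller part.

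**A reader might expect a paired test to rescue the comparison.** That depends on an unstated sample size and effect. At a 1-dermatome shift with 10 patients it would usually miss the difference too.

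**A reader might conclude that pooled KS is bound to reject falsely.** Placing one identical curve on both schedules does give rejection rates of up to 100%, but that puts a single-dose decay on a 24-hour infusion schedule. It is not a rate for this trial. Only the mixing of schedule and regimen carries over.

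**The stakes are limited.** This objection stands. Coverage is a secondary measurement, no stated sample size or decision rule depends on these tests, and the curves, C_max and T_max can be reported regardless. None of this makes the two phases independent or names the variable.

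**Conclusion.** Wrong as written and worth correcting, but not a threat to the descriptive pharmacokinetic aim. Two conclusions need no assumptions: the independence requirement fails for both the KS test and the unpaired t-test, and the KS variable is unspecified.

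The size depends on the reading. For coverage, under the assumptions shown, KS power is about 10%-12% against 74%-90% for a within-patient test, and most of the difference is due to KS on small tied counts. For pooled concentrations, a p-value cannot be attributed to regimen. The unpaired t-test is too conservative whenever the within-patient correlation is positive.

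No paired analysis removes the fixed order. A coverage difference would still combine regimen with time since surgery.

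**What to change.** In Data analysis:

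- Name the variable and drop the two-sample KS test.
- Coverage: use a within-patient test, for example the exact Wilcoxon signed-rank test, on each patient's number of blocked dermatomes, 60 minutes after the bolus against 24 hours of infusion. Give an estimate with 95% CI, and state how ties and zeros are handled.
- Concentrations: report the bolus and infusion curves separately and descriptively, with no test on pooled values.
- C_max: replace the unpaired t-test with a within-patient comparison labelled exploratory.
- T_max: report descriptively for each phase. Its contrast is largely set by the regimens and their sampling windows (4 hours against 24 hours), so a paired test would only make a contrast built into the design look more significant.
- State that the order is fixed, so regimen cannot be separated from time since surgery, and that bolus residue may affect early infusion levels.

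The cost is a rewording and a few lines of code, with no new data. The downside is that the concentration curves and T_max carry no formal p-value.

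### The unpaired t-test for C_max and T_max does not fit a design in which each patient who completes the protocol supplies both a bolus and an infusion value

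*Combined protocol and SAP*

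**What the plan says.** The Data analysis section treats bolus and infusion as two arms. For the peak concentration and its timing it names one test: "T_{max} and C_{max} of the two arms will be analyzed with an unpaired t-test".

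The Methods describe one group of patients measured in two consecutive phases:

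- Description of procedures, on the ESP block: "Randomization is not required because all participants will be undergoing the same protocol".
- Research protocol, part 1: "the investigator will administer 25 cc 0.25% ropivacaine through each nerve catheter (totaling 50 cc 0.25% ropivacaine"), followed by blood samples at "10 minutes, 15 minutes, 30 minutes, 45 minutes, 60 minutes, 90 minutes, 2 hours, and 4 hours".
- Research protocol, part 2: "at the 4-hour interval (4 hours after the initial bolus), both nerve catheter infusions will be resumed", followed by samples at "60 minutes, 2 hours, 4 hours, 8 hours, 12 hours, 24" hours.

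Pairing, a patient effect or a repeated-measures model is mentioned nowhere.

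**The concern.** A participant who completes both parts contributes one bolus C_max and one infusion C_max, and likewise two T_max values. These are pairs from the same person, hours apart, through the same catheters. The unpaired t-test assumes that the two sets of values come from independent people.

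If a patient with a high bolus peak also tends to have a high infusion peak, which is plausible for C_max, the unpaired standard error is too large. Confidence intervals are then too wide and a real difference is more likely to be missed. If the correlation were negative, the standard error would be too small and false positives would rise. In both cases the reported standard error, interval and p-value do not match the design. This is the only test the plan names for comparing C_max and T_max between phases.

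**Working it through.** **Inputs.** The design facts come from the Methods, as quoted above. The documents give no sample size, SDs, correlation, effect size or significance level, so there is no planned figure to reproduce. Everything below that needs such a value assumes it: n = 10 or 20 complete pairs, within-patient correlation ρ from −0.3 to 0.7, SD ratio k = 1 or 3, two-sided 5% level.

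**Step 1: standard error.** With n pairs and SDs s₁ and s₂:

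- true variance of the mean difference = (s₁² + s₂² − 2ρs₁s₂)/n
- variance that the unpaired test estimates = (s₁² + s₂²)/n, for both the pooled and the Welch form when the two group sizes are equal
- ratio of unpaired to true standard error = √[(1 + k²)/(1 + k² − 2ρk)]

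For example, ρ = 0.5 with k = 1 gives √(2/1) = 1.41, and with k = 3 gives √(10/7) = 1.20.

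**Step 2: interval width.** Pairing uses n − 1 degrees of freedom instead of 2n − 2. At n = 10 the critical values are 2.26 (9 df) and 2.10 (18 df). The width ratio, unpaired to paired, is the standard error ratio times t(2n−2)/t(n−1), which is about 0.93 here.

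| ρ | SE ratio, k=1 | SE ratio, k=3 | CI width ratio, k=1, n=10 | CI width ratio, k=3, n=10 |
|---|---|---|---|---|
| −0.3 | 0.88 | 0.92 | 0.81 | 0.85 |
| 0 | 1.00 | 1.00 | 0.93 | 0.93 |
| 0.3 | 1.20 | 1.10 | 1.11 | 1.03 |
| 0.5 | 1.41 | 1.20 | 1.31 | 1.11 |
| 0.7 | 1.83 | 1.31 | 1.70 | 1.22 |

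The paired interval is the narrower one only when ρ exceeds [1 − (t(2n−2)/t(n−1))²](1 + k²)/(2k). That is about 0.14 (k = 1) or 0.23 (k = 3) at n = 10, and 0.06 or 0.11 at n = 20.

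**Step 3: type I error.** Simulation of bivariate normal data, 200,000 trials per setting, unpaired test at n = 10:

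| ρ | Pooled, k=1 | Pooled, k=3 | Welch, k=3 |
|---|---|---|---|
| −0.3 | 8.4% | 7.9% | 6.9% |
| 0 | 4.9% | 5.9% | 5.1% |
| 0.3 | 2.3% | 4.0% | 3.4% |
| 0.5 | 1.0% | 2.9% | 2.4% |
| 0.7 | 0.2% | 2.0% | 1.6% |

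The pooled column at k = 3 mixes two effects. At ρ = 0 its standard error is right, and the excess over 5% comes from the unequal variances; the Welch column largely removes this. The paired test stayed between 4.9% and 5.1% in all 24 settings. A separate simulation agreed to within about 0.2 percentage points (for example 8.2% at ρ = −0.3, k = 1).

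**Step 4: power.** Assumed difference 0.8 × √[(s₁² + s₂²)/2], unpaired pooled versus paired:

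| ρ | n=10, k=1 | n=10, k=3 | n=20, k=1 | n=20, k=3 |
|---|---|---|---|---|
| 0.3 | 0.38 vs 0.48 | 0.40 vs 0.42 | 0.73 vs 0.82 | 0.71 vs 0.76 |
| 0.5 | 0.37 vs 0.62 | 0.39 vs 0.48 | 0.76 vs 0.92 | 0.72 vs 0.82 |
| 0.7 | 0.35 vs 0.83 | 0.39 vs 0.55 | 0.80 vs 0.99 | 0.74 vs 0.88 |

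At ρ = 0, n = 10, k = 1, pairing costs a little: 0.40 unpaired against 0.36 paired.

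**Step 5: incomplete pairs.** Suppose 20 participants give bolus values and 16 of them also give infusion values, with unit SDs and ρ = 0.5. The unpaired standard error is √(1/20 + 1/16) = 0.335. The true one is √(1/20 + 1/16 − 2 × 0.5/20) = 0.250. The ratio is 1.34, and the simulated type I error is 1.1%. Some missing infusion data therefore do not make the unpaired test right.

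**The case against.** The best counter-argument concerns weight, because the mismatch itself is plain from the documents.

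- **The likely error is conservative and the main output is descriptive.** Aim 1 is to produce curves with their C_max and T_max, and states no hypothesis. The plan says of the results that "The data for this sheet can then be used for statistical analysis and creation of a pharmacokinetic profile for the ESP block". Curves and per-phase summaries are identical under either test, as is the mean difference in complete pairs. This stands and limits the harm. But the title announces a comparison, and the Data analysis section commits to a test.
- **No magnitude comes from the documents.** This also stands. The illustrations run from a small benefit of the unpaired test (ρ near zero) to a large loss (ρ = 0.7 with equal SDs). The power loss depends on the assumed difference too: at n = 10, equal SDs, ρ = 0.5 and a 2 SD difference, both tests exceed 0.99.
- **For T_max the pairing is secondary.** The two sampling schedules share only 1, 2 and 4 hours, so the schedules themselves constrain any T_max difference. No size of error is claimed for T_max, and a signed-rank test has the same limit.
- **Pairing does not make the comparison clean.** The order is fixed, and of the level at the start of the infusion the plan says only: "It is expected that at the 4-hour interval, the serum ropivacaine level will be approaching or have reached the baseline level". A paired test gives a valid standard error for a difference that may still contain order and carry-over effects.
- **The Kolmogorov-Smirnov and logrank tests in the same section also assume independence.** True. Changing only the t-test would leave the section inconsistent, which is a reason to look at them as well.

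None of these points makes the unpaired test correct for this design.

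**Conclusion.** The concern holds. That the test does not fit the design follows from the documents alone; how much it matters depends on values they do not give. Under the assumed range, a positive correlation of 0.3 to 0.7 inflates the standard error 1.20 to 1.83 times with equal SDs, or 1.10 to 1.31 times with a 3:1 SD ratio. At −0.3 it is understated (0.88 and 0.92 times). With equal SDs or the Welch form, ignoring a positive correlation adds no false positives. The pooled form with unequal SDs can slightly exceed 5% at small ρ (5.3% at ρ = 0.1, k = 3, n = 10) because of the unequal variances.

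The damage is confined to the bolus-versus-infusion inference on C_max and T_max. It should be fixed because the correction is almost free, but it does not threaten the descriptive pharmacokinetic profile.

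**What to change.** Replace the unpaired t-test sentence in the Data analysis section with text along these lines:

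> C_max will be compared between the bolus and infusion phases within patients, using a paired t-test and a 95% confidence interval for the mean difference. T_max will be reported as within-patient differences with median and range; if a test is wanted, the Wilcoxon signed-rank test will be used. Because the two phases are sampled on different schedules (10 minutes to 4 hours and 1 to 24 hours), the observable T_max values are restricted. The fixed order of bolus then infusion, and possible carry-over, are not removed by pairing.

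A log scale for C_max is optional. If participants with only one phase are to contribute, name a mixed model with a random patient effect instead of the paired test. Review the Kolmogorov-Smirnov and logrank sentences at the same time, so that the section describes the phases consistently.

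The cost is a few sentences, with no new data, patients or procedures. The downsides are fewer degrees of freedom (9 instead of 18 at n = 10), a slightly wider interval if the correlation is below the break-even values above, and the loss of participants with one phase only unless the mixed model is used.
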